Participants will report to the laboratory (VA bldg. 2 room 1D21) at ~ 0800 in a fasted state, having abstained from caffeine and exercise for the past 12 hours. Catheters may be placed in the leg (common femoral artery and femoral vein) or arm (brachial artery and antecubital vein) by a licensed physician using standard sterile technique. During the catheterization process endothelial cells may be collected using the sterile J-wire (see Participants Instrumentation for more detailed description of this procedure). It should be noted that the insertion of the J-wire is common practice for catheter placement. Following placement of catheters, resting measurements of arterial blood pressure, heart rate, and limb blood flow (ultrasound Doppler) will be taken, and resting blood samples (arterial and venous) may be collected. Control measures may be made at rest, during passive limb movement, exercise, and immediately following exercise during post exercise circulatory occlusion (PECO). Protocol 4 is nearly identical to protocol 1 with the potential addition of flow mediated dilation (FMD) to assess vascular function in the popliteal, femoral or brachial artery. The FMD will be performed in accordance with recently published guidelines ²² employing distal cuff placement for 5 min at 250 mmHg and continuous assessment of arterial diameter for 2 min following cuff release using edge detection software. All measures will first be performed in the control condition. During each work bout the following sequence of events may be conducted (as indicated by the arrows in the timeline below): (1) sampling of arterial and venous blood for the direct measurement of free radicals, blood gases, and markers of oxidative stress (ascorbic acid, glutathione, lipid hydroperoxide, 8-isoprostanes, nitrite/nitrate, ferric reducing ability of plasma). (2) continuous measurement of central hemodynamics (heart rate, stroke volume, cardiac output) and arterial and venous pressures, and (3) femoral blood flow via ultrasound Doppler. After a 120 min recovery, the protocol may be repeated following administration of an oral antioxidant cocktail (AOC, consisting of 1000 mg vitamin C, 600 IU vitamin E, and 600 mg alpha lipoic acid) or infusion of vitamin C (range 1 to 5 grams). We have previously reported reduced oxidative stress, diminished free radical levels, and improved vascular function with this AOC ²³⁻²⁷. Moreover, this 120 min period is of sufficient duration to allow for vitamin absorption into the circulation. Endothelial cells (if collected using the J-wire technique during catheterization for Specific Aims 1, 2, and 3), may be measured for nitrotyrosine, NAD(P)H oxidase, xanthine oxidase, superoxide dismutase, catalase, nuclear factor-KB (NF-KB).

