Flow Mediated Dilation (FMD): After 15-20 minutes in the supine position a blood pressure cuff will be placed on the lower leg or forearm. Ultrasound images of the artery and Doppler waveforms will be obtained prior to cuff inflation (baseline). The cuff will then be inflated to 250mmHg for 5 minutes. Following the cuff release, ultrasound images of the popliteal artery and Doppler waveforms will be recorded continuously for 2 minutes. During this time, arterial images during diastole will be captured by image analysis software (Medical Imaging Applications). All recorded ultrasound images and velocity spectra segments will be saved to the GE Logiq 7 hard drive for off-line image and waveform analysis. The time averaged, and intensity-weighted mean blood velocity (Vmean) will be averaged across 5 second intervals for the entire 2 minute clip following cuff release. In addition, edge detecting software will be utilized to measure arterial diameter frame by frame, which will also be averaged into 5 second intervals. Summed shear rate throughout the 2 minutes will be calculated based on vessel diameter and blood velocity. The maximum change in vessel diameter, relative to baseline, will be determined and expressed as %FMD and %FMD/summed shear rate. A greater FMD response is an indicator of healthier vessels. A typical response for a young healthy participants would be 8 - 12% or greater dilation, whereas a poor response would be <5%. In addition, it is also important to be able to express the change in diameter relative to shear stress, as the shear stress is the stimulus for the NO-induced dilation. Again, greater FMD/shear values are indicative of healthier vessels.

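### The FMD/shear index divides peak dilation by shear from the whole 2-minute recording, including shear after the peak, which contradicts the plan's own reason for normalising

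*Combined protocol and SAP*

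**What the plan says.** The method is in the Flow Mediated Dilation (FMD) entry under Participant Instrumentation. Mean velocity "will be averaged across 5 second intervals for the entire 2 minute clip following cuff release". Diameter is measured frame by frame, "which will also be averaged into 5 second intervals". Then "Summed shear rate throughout the 2 minutes will be calculated based on vessel diameter and blood velocity", and "The maximum change in vessel diameter, relative to baseline, will be determined and expressed as %FMD and %FMD/summed shear rate". The reason given for expressing dilation relative to shear is "as the shear stress is the stimulus for the NO-induced dilation", and the reader is told that "greater FMD/shear values are indicative of healthier vessels". Numerical benchmarks are given for raw FMD only; for the ratio, only the direction is stated.

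FMD enters the trial in Protocol 4, which is described as Protocol 1 "with the potential addition of flow mediated dilation (FMD) to assess vascular function in the popliteal, femoral or brachial artery", with measures in a control condition that may be repeated after antioxidant. Statistical Methods, Data Analysis and Interpretation sets out a model for the EPR and says that other variables will be handled comparably, without detail. No section says which of the two FMD indices decides the comparison.

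**The concern.** The denominator is meant to represent the stimulus that produced the peak. Summed over the full recording, it represents that only if the peak falls in the last 5-second interval. Otherwise it also contains shear that came too late to contribute. Two arteries with the same stimulus and the same dilation can then receive different scores because of what happened after the peak, and the plan reads the higher score as the healthier vessel.

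A second, separate weakness is the ratio form. Dividing by shear removes its influence only when FMD is strictly proportional to shear. With a non-zero intercept, a difference in shear leaks into the index whichever window is used.

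At stake is the reading of one of two FMD indices, in the comparison of hypertensive with normotensive participants and in the comparison before and after antioxidant.

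**Working it through.** The plan gives no shear value, time to peak or FMD standard deviation, so it has no figure to reproduce here. All shear inputs below are assumptions. From the documents come the 2-minute window, the 5-second intervals (120/5 = 24), an 8% dilation (the lower end of the plan's typical range for young healthy participants) and 20 participants per group.

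**1. Share of the sum that falls after the peak.** Assume relative shear at time t of 0.15 + 0.85·exp(−t/τ), with τ from 15 to 40 s and the peak at T.
- Total = 0.15·120 + 0.85·τ·(1 − exp(−120/τ)).
- After peak = 0.15·(120 − T) + 0.85·τ·(exp(−T/τ) − exp(−120/τ)).

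| τ (s) | T (s) | Total | After peak | Share |
|---|---|---|---|---|
| 15 | 45 | 30.75 | 11.88 | 39% |
| 15 | 75 | 30.75 | 6.83 | 22% |
| 40 | 45 | 50.31 | 20.60 | 41% |
| 40 | 75 | 50.31 | 10.27 | 20% |

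A share is not yet a bias. It becomes one only if the post-peak part differs between the things compared.

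**2. Effect of the window alone.** Assume shear of 100 + 700·exp(−t/30) per second up to a peak at 50 s. Over the ten 5-second intervals to the peak, the sum is 22,014. Give both groups this same sum and the same 8% dilation, and vary only mean shear over the remaining 70 s.
- Post-peak shear 100/s: 8/(22,014 + 7,000) = 2.76 × 10⁻⁴.
- 150/s: 8/(22,014 + 10,500) = 2.46 × 10⁻⁴, which is 11% lower.
- 200/s: 8/(22,014 + 14,000) = 2.22 × 10⁻⁴, which is 19% lower.
- To-peak index in every case: 8/22,014 = 3.63 × 10⁻⁴.

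The full-window index thus shows a deficit of 11% or 19% where neither dilation nor stimulus differs. In simulated trials whose groups differed only in post-peak shear, the full-window index declared a group difference in 17% to 54% of trials, depending on the assumed inputs. The to-peak index did so in about 5%.

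**3. When nothing goes wrong.** With equal curves and peak times, dilations of 8% and 6% over a common full sum of 32,592 give 2.45 and 1.84 × 10⁻⁴. That is the same 25% deficit as in raw %FMD.

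**4. The ratio form, whatever the window.** If FMD = a + b·S, then FMD/S = b + a/S, which is free of S only when a = 0. Assume b = 2 and mean shear of 3.0 in one group and 2.2 in the other (27% less), with the same line in both. At these means:
- a = 0: 2.00 and 2.00.
- a = 2: 2.67 and 2.91.
- a = 4: 3.33 and 3.82.
- a = −2: 1.33 and 1.09, so the direction flips.

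With 20 per group, shear SD 0.6 and residual SD 1.5, a t-test on the ratio rejected in about 5% of simulated trials at a = 0, 22% to 24% at a = 2 and 57% to 58% at a = 4. With 13% less shear it rejected in 9% (a = 2) and 18% (a = 4). With shear as a covariate the rate stayed at about 5%. Raw %FMD rejected in about 73% at the 27% gap, because it makes no allowance for shear.

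**The case against.** A reader might infer that the vascular comparison as a whole will be distorted, or that hypertensive vessels will come out as the healthier ones. The documents do not support that.
- Raw %FMD is reported beside the ratio and does not depend on the window, so only one of two indices is exposed.
- Reversal needs a large gap. In the setting of step 2, with dilations of 8% (normotensive) and 6% (hypertensive) and hypertensive post-peak shear of 100/s, the ratio reverses only if normotensive post-peak shear exceeds (8 × 29,014/6 − 22,014)/70 ≈ 238/s.
- Background and Introduction describes impaired muscle blood flow during exercise. It does not say that shear after cuff release is lower in hypertension, or by how much.

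A reader might also take the 22% to 58% in step 4 as evidence against the 2-minute window. It is not: that simulation gives each participant one shear value with no time course, so it tests the ratio against a covariate. The evidence on the window is step 2.

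Three further objections stand in part.
- Summing to the peak is not a complete cure. If shear itself decays faster in one group (τ of 15 against 30 s, dilations 6% against 8%), both ratios reverse: full window 2.67 against 2.45, to-peak 3.98 against 3.63 (× 10⁻⁴).
- The covariate is not perfect. At an assumed shear reliability of 0.7 it rejects in 12% to 13% of trials. If hypertension acts partly by lowering shear, adjustment removes part of the disease effect.
- Protocol 4 says that FMD follows published guidelines. These are not among the documents, so whether they support the full window could not be checked.

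None of this removes the inconsistency between the stated stimulus and the stated denominator.

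**Conclusion.** The point holds as a minor improvement. It follows from the text alone that post-peak shear enters the denominator unless the peak falls in the last interval, and that this contradicts the plan's reason for normalising. The size depends on assumptions: roughly 20% to 40% of the sum lies after a peak at 45 to 75 s, and a false deficit of 11% to 19% arises if mean post-peak shear is 150 to 200/s in one group and 100/s in the other. With equal shear curves and peak times there is no distortion. The ratio form is a separate weakness that vanishes if the intercept is zero or shear is equal. FMD is optional in Protocol 4 and the EPR analysis is unaffected.

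**What to change.** - Sum shear from cuff release to the time of peak diameter, using the 5-second values already planned.
- Continue to report raw %FMD, and state before analysis which FMD result is the main one.
- Add an analysis of %FMD with the to-peak shear sum as a covariate. Specify its model for FMD, with group and condition (control, antioxidant) and participant as the repeated unit. The EPR model cannot be carried over unchanged, because it contains exercise stage and FMD has none.
- If the ratio is kept, report it as descriptive and rest no conclusion on it alone.

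The cost is a paragraph in the SAP, a re-cut of recorded data and one covariate; no new measurement is needed. The drawback is that adjustment may remove part of a disease effect that acts through shear, so unadjusted %FMD should be shown alongside.
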